1. AMENDMENTS FROM PREVIOUS VERSION(S)

This is the third version of the statistical analysis plan, based on the BBI608-201GBM protocol dated March 9th, 2017 [1]. The major changes in this amendment are editing dosing intensity and compliance section, adding some abbreviations, adding back the PD/Biomarker analysis section, rearranging the secondary objectives by phase, adding language regarding sponsor terminated follow-up, adding information about last dose of study treatment, and elaborating on the statistical methodology for PFS, DCR and ORR used in the statistical analyses section.

2. INTRODUCTION

2.1. Study Design

Phase Ib

This is an open-label, multi-center, phase Ib/II study of BBI608 administered in combination with temozolomide (TMZ) to patients with recurrent or progressive GBM who have not received prior bevacizumab therapy. The study is designed to explore the safety, tolerability and pharmacokinetics of BBI608, and to define a recommended phase 2 dose (RP2D) of BBI608 when administered in combination with TMZ.

ARM A: Patients who are candidates for surgical resection will receive BBI608 as monotherapy prior to resection, followed by post-operative BBI608 administered in combination with TMZ.

BBI608 will be administered at a dose-level of 480 mg twice daily for 7 (± 2) days prior to a planned surgical resection or biopsy of recurrent GBM. BBI608 will be discontinued immediately prior to the surgical procedure and will remain discontinued pending clinical post-operative recovery of the patient.

Upon the clinical recovery of the patient and at a time between 15-28 days following surgery, BBI608 will be administered orally, daily, in combination with temozolomide that is administered at 150 mg/m² for days 1 through 5 of each 28-day cycle. The dose of temozolomide can be increased to 200 mg/m² as per standard TMZ dosing guidelines for patients who complete at least one cycle at 150 mg/m². The initial dose of BBI608 will be 480 mg twice daily. Dose adjustment is allowed.

Pre-Operative Period BBI608 monotherapy	SURGERY/BIOPSY	Post-Operative Period BBI608 with TMZ
BBI608 will be administered orally, daily, at a dose-level of 480 mg twice daily for 7 (± 2) days prior to a scheduled resection for recurrent GBM.		BBI608 will be administered orally, daily, at a dose-level of 480 mg twice daily in combination with TMZ 150 mg/m ² that is administered on days 1 through 5 of each 28-day cycle. Cycles will repeat until disease progression or another discontinuation criterion is met.
Approximately 7 (± 2) days		Begins between 15-28-days after surgery

ARM B: Patients who are not candidates for surgical resection will receive BBI608 administered orally, daily, in combination with temozolomide 150 mg/m² that is administered on days 1 through 5 of each 28-day cycle. The dose of temozolomide can be increased to 200 mg/m² as per standard TMZ dosing guidelines for patients who complete at least one cycle at 150 mg/m². The initial dose of BBI608 will be 480 mg twice daily. Dose adjustment is allowed.

For patients in Arm A during the run-in period with BBI608 monotherapy, the same DLT rules as for the combination therapy will apply. Enrollment will be held if ≥ 2 of 6 patients are unable to undergo resection due to DLTs. Enrollment will also be held if ≥ 2 of 6 patients have an unexpected surgical complication.

Initial enrollment will be to a 6-patient safety cohort in each arm. These patients will be evaluated for the occurrence of DLT during the first 28 days of combination treatment with BBI608 and TMZ. If DLT is observed in ≥ 2 of 6 patients evaluable for DLT, the initial dose of BBI608 for all patients in that arm will be reduced to the next lower dose level of 240mg twice daily, and an additional 6-patient safety cohort will be enrolled at that dose-level and evaluated for DLT as above. Enrollment will continue at a dose-level at which ≤ 1 of 6 patients experiences DLT. Dose modification is allowed according to the standard schedule for BBI608.

Cycles of therapy will consist of the patient taking BBI608 daily in combination therapy for 28 days. Tumor assessments will be performed every two cycles (eight weeks), or as otherwise clinically indicated.

The RP2D is defined as the dose level at which no more than one patient with DLT is observed among six patients. Once the RP2D has been reached for a given arm based on

DLT assessment rules outlined above, up to 24 additional evaluable patients may be enrolled at RP2D.

It is expected that up to 30 patients (including those enrolled to the DLT evaluation cohorts) will be enrolled in each arm.

Phase II

In both Phase Ib and Phase II, a study cycle will consist of 28 days of daily administration of BBI608 and TMZ administration on days 1-5 of each cycle. Pharmacokinetic (PK) and pharmacodynamic assessments will be performed in the first cycle only. Safety and tolerability of BBI608 in combination with TMZ will be assessed for the duration of the study treatment and for 30 days after the last dose of BBI608. Evaluation of anti-tumor activity of BBI608 in combination with TMZ will be performed at 8-week intervals while patients remain on study according to RANO.

Patients will continue treatment with BBI608 and TMZ until the investigator has determined that they are no longer clinically benefiting due to progression of disease, or unacceptable toxicity, or until another discontinuation criterion is met. Treatment with BBI608 as monotherapy can continue if TMZ is discontinued for any reason. Also, the investigator may continue BBI608 in combination with TMZ or BBI608 monotherapy after the initial demonstration of radiological progression and in the absence of intolerable toxicities, performance status decline, worsening of disease related symptoms, radiographical findings that would warrant acute intervention and no ongoing severe toxicities that may be related to BBI608. The patient will also get repeat tumor assessments after 4-6 weeks.

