
Criteria for Determination of Dose-Limiting Toxicity:
	
A DLT is defined by the occurrence of any of the following toxicities possibly, probably or definitely related to BBI608 or to BBI608 in combination with TMZ during the first 28 days of combination treatment:
 
 •CTCAE Grade 3 thrombocytopenia with clinically significant bleeding •CTCAE Grade 4 hematological toxicity. •CTCAE Grade 3 non-hematological toxicity, except: 
 ○ Grade 3 nausea, vomiting, anorexia, diarrhea or fatigue that persist <7 days with appropriate supportive care. •CTCAE Grade 4 non-hematological toxicity 
 ○ Because DVT and PE are common complications among GBM patients, the first occurrence of DVT or PE will not be considered a DLT. •Toxicities leading to delay of study treatment for ≥ 14 days •During the post-surgical period and prior to initiation of combination therapy with BBI608 and TMZ, any grade 3 or greater hematological or non-hematological toxicity that cannot be attributed to the surgical procedure or to typical post-operative complications •Any other toxicity that in the view of the Principal Investigator represents a clinically significant hazard to the patient 
Whether a DLT has occurred will be assessed during the first 28 days of combination therapy. DLTs will be determined from adverse events, and changes from baseline in physical examination findings and in laboratory parameters. Patients who do not complete 28 days of combination therapy for reasons other than DLT may be replaced.
 
Adverse events considered related to TMZ only will not be considered DLTs for BBI608 in combination with TMZ.

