4.4 Criteria for Dose Escalation and Determination of Dose-Limiting Toxicity

Dose-Limiting Toxicity (DLT) will be evaluated separately in each study arm. Patients evaluable for DLT assessment are defined as having been exposed to at least 28 days of continuous daily administration of BBI608 in combination with TMZ (i.e. DLT evaluation period starts from the first administration of TMZ), or having had a protocol-defined DLT at any time within this period. Based on the tolerability and safety of evaluable patients, enrollment of additional patients will occur according to criteria described below:

- If ≤ 1 treated patients experience a BBI608-related DLT (defined below) by Day 28 of Cycle 1 of combination therapy with TMZ, then additional patients will be enrolled at this BBI608 dose into the RP2D expansion cohort.
- If ≥ 2 treated patients at a dose level experience a BBI608-related DLT by Day 28 of Cycle 1, patient enrollment into this BBI608 dose level cohort will stop and the BBI608 dose will be reduced to the next lower dose level of 240mg twice daily. An additional 6-patient safety cohort will be enrolled at the reduced dose-level and evaluated for DLT.
- RP2D of BBI608 with TMZ will be defined as the dose level at which no more than one patient with DLT is observed among six patients.

The BBI medical Monitor and Principal Investigator will review all significant BBI608-related toxicities to determine whether the initial BBI608 dose (480 mg twice daily) requires adjustment. Lower BBI608 doses may be assigned after agreement between the BBI Medical Monitor and the Principal Investigator.

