4.5 Dose-Limiting Toxicity

A DLT is defined by the occurrence of any of the following toxicities possibly, probably or definitely related to BBI608 or BBI608 in combination with TMZ during the first 28 days of combination treatment:

- CTCAE Grade 3 thrombocytopenia with clinically significant bleeding
- CTCAE Grade 4 hematological toxicity.
- CTCAE Grade 3 non-hematological toxicity, except:
 - Grade 3 nausea, vomiting, anorexia, diarrhea or fatigue that persist < 7 days with appropriate supportive care.
- CTCAE Grade 4 non-hematological toxicity
 - Because DVT and PE are common complications among GBM patients, the first occurrence of DVT or PE will not be considered a DLT.
- Toxicities leading to delay of study treatment for ≥ 14 days
- During the post-surgical period and prior to initiation of combination therapy with BBI608 and TMZ, any grade 3 or greater hematological or non-hematological toxicity that cannot be attributed to the surgical procedure or to typical post-operative complications
- Any other toxicity that in the view of the Principal Investigator represents a clinically significant hazard to the patient

Whether a DLT has occurred will be assessed during the 28 days of the first cycle of combination treatment with TMZ and during the run in and post-operative period of Arm A. DLT will be determined from adverse events and changes from baseline in physical examination findings and in laboratory parameters.

To be considered evaluable for DLT, compliance with the assigned dose of BBI608 and TMZ must be $\geq 80\%$. Patients who do not complete 28 days of combination therapy for reasons other than DLT or patients who are not eligible for DLT assessment may be replaced. Adverse events considered related to TMZ only will not be considered DLTs for BBI608 in combination with TMZ.

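### Protocol 4.4 leaves an Arm A patient with a DLT before combination therapy outside the evaluable set for the 2-of-6 rule, while protocol 4.5 assesses that period for DLTs

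*SAP*

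**What the plan says.** Arm A patients take BBI608 alone for 7 (±2) days, have surgery, and start BBI608 plus TMZ 15 to 28 days later. The first six are a safety cohort. Two or more DLTs among six patients evaluable for DLT lower the starting dose to 240 mg twice daily; at most one leaves 480 mg as the recommended Phase 2 dose.

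The documents describe the DLT period in several ways:

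- **Protocol 4.4** is confined to combination therapy: "DLT evaluation period starts from the first administration of TMZ". A patient is evaluable after 28 days of combination, or after a DLT inside that period. The decision bullets in the same section are worded more widely and refer to "treated patients at a dose level experience a BBI608-related DLT by Day 28 of Cycle 1".
- **Protocol 4.5** opens with the first 28 days of combination. It then lists a criterion that can only be met earlier ("During the post-surgical period and prior to initiation of combination therapy with BBI608 and TMZ"), and later says DLTs are assessed in cycle 1 "and during the run in and post-operative period of Arm A".
- **The protocol synopsis and SAP 2.1** are mixed. Both assess the cohort over the first 28 days of combination ("These patients will be evaluated for the occurrence of DLT during the first 28 days of combination treatment with BBI608 and TMZ"). Both also say that in the run-in "the same DLT rules as for the combination therapy will apply". The synopsis lists the post-surgical criterion as well.
- **SAP 3.1.1** takes its DLT definition from protocol 4.5.

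On replacement, the synopsis says: "Patients who do not complete 28 days of combination therapy for reasons other than DLT may be replaced". Protocol 11.3 agrees. Protocol 4.5 adds a second group: "for reasons other than DLT or patients who are not eligible for DLT assessment may be replaced".

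Protocol 10.6 plans DLT incidence in all patients enrolled into a safety cohort. SAP 8.2.2.1 plans DLT listings by arm, with no count, denominator or period.

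**The concern.** DLT is the Phase Ib primary endpoint and sets the Arm A dose. The 2-of-6 rule needs a numerator and a denominator. Protocol 4.5 lets a run-in or post-operative DLT into the numerator. Protocol 4.4, which defines who is evaluable, leaves the same patient out of the denominator if TMZ is never started. If the patient does go on to complete 28 days of combination, 4.4 judges that patient on the later window only.

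A cohort with one run-in DLT and one combination DLT can then be counted in two ways. If both count, it is 2 of 6 and the dose falls to 240 mg. If the run-in patient is treated as not evaluable and replaced, it is 1 of 6 and 480 mg stands unless the medical monitor and Principal Investigator decide otherwise under 4.4. The only consequence the plan ties specifically to run-in DLTs is an enrollment hold when two or more patients cannot undergo resection. One such patient does not trigger it.

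**Working it through.** **1. The texts compared for one patient: a run-in DLT, stopped before TMZ**

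| Source | Is it a DLT? | Evaluable, or counted? |
|---|---|---|
| Protocol 4.4, evaluability definition | Outside the period | Not evaluable |
| Protocol 4.4, decision bullets | BBI608-related, before Day 28 of cycle 1 | Can be read as counted |
| Protocol 4.5, assessment sentence | Yes | Not stated |
| Protocol 4.5, 80% compliance with BBI608 and TMZ | Not addressed | Hard to meet if TMZ was never given |
| Synopsis and protocol 11.3, replacement | Not addressed | Replacement only for reasons other than DLT |
| Protocol 4.5, replacement, second clause | Not addressed | Replaceable if not eligible for DLT assessment |
| Protocol 10.6 | Not addressed | In the denominator: all enrolled cohort patients |
| SAP 2.1, de-escalation rule | Same rules in the run-in | Only patients evaluable for DLT, a term the SAP does not define |

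No sentence says outright whether this patient counts.

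**2. The plan's own figures**

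SAP 4.2.1.3 gives 91%, 71%, 49%, 31% and 17% at true DLT rates p of 0.1 to 0.5. They reproduce as (1−p)³ + 3p(1−p)²·(1−p)³ = 0.906, 0.709, 0.494, 0.309, 0.172. That is a three-plus-three rule and does not address the Arm A window. The flat six-patient rule in the text, (1−p)⁶ + 6p(1−p)⁵, gives 0.886, 0.655, 0.420, 0.233, 0.109. That difference is a separate matter; the flat rule is used below.

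**3. Effect of the choice**

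The documents give no DLT rates. Let q be the rate before combination (run-in or post-operative) and r the rate in combination cycle 1. Both are assumed, and taken as independent.

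- Counted: p = 1 − (1−q)(1−r), and P(pass) = (1−p)⁶ + 6p(1−p)⁵.
- Not counted: P(pass) = (1−r)⁶ + 6r(1−r)⁵.

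Example with r = 0.10 and q = 0.03: p = 1 − 0.97 × 0.90 = 0.127.
- Counted: 0.873⁶ + 6 × 0.127 × 0.873⁵ = 0.443 + 0.386 = 0.829.
- Not counted: 0.9⁶ + 6 × 0.1 × 0.9⁵ = 0.531 + 0.354 = 0.886.

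| r | Not counted | Counted, q = 1% | Counted, q = 3% | Gap in points (q = 1%, 3%) |
|---|---|---|---|---|
| 5% | 96.7% | 95.5% | 92.5% | 1.2, 4.2 |
| 10% | 88.6% | 86.8% | 82.9% | 1.8, 5.7 |
| 15% | 77.6% | 75.6% | 71.5% | 2.0, 6.1 |
| 20% | 65.5% | 63.6% | 59.7% | 2.0, 5.9 |

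The chance that the question arises at all is 1 − (1−q)⁶: 5.9% at q = 1% and 16.7% at q = 3%.

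**4. Does the resection hold cover it?**

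The chance of two or more pre-combination DLTs in six is 1 − (1−q)⁶ − 6q(1−q)⁵: 0.1% at q = 1% and 1.2% at q = 3%. This is an upper limit for the hold, which counts only DLTs that prevent resection.

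**5. Higher rates**

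At r = 10%, the counted pass probability is 78.8%, 68.0% and 57.0% for q = 5%, 10% and 15%. Against 88.6%, the gaps are 10, 21 and 32 points.

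**The case against.** The strongest reply is that the plan, read as a whole, already counts these events. SAP 3.1.1 points to protocol 4.5, which names the run-in and post-operative period. The synopsis and SAP 2.1 apply the DLT rules to the run-in. Replacement is mostly limited to reasons other than DLT, and the 4.5 clause on patients not eligible for DLT assessment follows the 80% compliance sentence, so it may be aimed at non-compliance. The 4.4 bullets count treated patients up to Day 28 of cycle 1, and protocol 10.6 uses all enrolled cohort patients. Medical monitor review is a further safeguard. Run-in toxicity will also appear in the adverse event tables, which start from the first dose of either drug.

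Much of this stands. A reader might infer from the 28-day sentence that the synopsis and SAP 2.1 are confined to combination therapy. They are not: each is internally mixed, and only the period and evaluability definition in 4.4 is strictly limited to combination. Counting is the better-supported reading. But the 2-of-6 rule is applied to evaluable patients, and the definition of evaluable points the other way. The review in 4.4 is discretionary and fixes no count.

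A reader might also take the 32-point gap as the size of the problem. It needs a 15% pre-combination DLT rate, which the documents do not support. Protocol 1.7 reports 4 grade 3 events among 41 monotherapy patients (4/41 = 9.8% if each was a different patient), at up to 2000 mg/day over full exposure. All were diarrhea or fatigue, which 4.5 exempts when they last under 7 days with supportive care. That is not a DLT rate for a run-in of about a week. It says nothing direct about the post-operative period, but BBI608 is held then and 4.5 excludes toxicity attributable to surgery.

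Finally, SAP 8.1.1 says follow-up was terminated after 29JUN2018, so the dose decision may already have been made. That limits what a text change can do prospectively, but not the value of stating how the count was made.

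**Conclusion.** The point holds in a limited form. The evaluability definition in protocol 4.4 conflicts with the Arm A assessment period in 4.5. Applied literally, it could leave 480 mg in place after two DLTs. The weight of the text favours counting pre-combination DLTs, so this is one definition out of line with the rest, not a plan that ignores run-in toxicity.

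The size is modest: about 1 to 6 percentage points in the chance that 480 mg passes. This rests on assumed rates of 1-3% before combination and 5-20% during it, on independence, and on the flat six-patient rule. The documents do not show that any patient was in fact left out or that the Arm A dose was wrongly set. The change is still worth making, because the rule decides the dose and the ambiguity is cheap to remove.

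**What to change.** - **Protocol 4.4:** amend the evaluability definition so that, for Arm A, the DLT period runs from the first BBI608 dose through Day 28 of combination cycle 1. State that a patient with a run-in or post-operative DLT is evaluable, counts in the 2-of-6 rule and is not replaced.
- **Protocol synopsis and SAP 2.1:** align the 28-day sentences with this.
- **SAP 8.2.2.1:** report the Arm A DLT count over its denominator, which also supplies the incidence planned in protocol 10.6. Show the period (run-in, post-operative, cycle 1) in the listing.
- **If the dose decision has already been made:** state in SAP 8.2.2.1 which count was used and whether any patient was replaced after a pre-combination DLT.

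The cost is a few sentences, one count and one listing column from data already collected, with no new visits. The downside is that a step down to 240 mg, with its extra six-patient cohort, becomes somewhat more likely. At assumed rates of 10% in combination and 3% before it, the chance rises from 1 − 0.886 = 11% to 1 − 0.829 = 17%.

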2.2. Study Objectives

2.2.1. Primary Objectives

Phase Ib:

To determine the safety, tolerability, and RP2D of BBI608 when administered in combination with temozolomide in adult patients with recurrent or progressed glioblastoma (GBM).

Phase II:

To assess the progression free survival (PFS) of BBI608 administered with TMZ at 6 months.

2.2.2. Secondary Objectives

Phase Ib:

- To determine the pharmacokinetic profile of BBI608 administered in combination with TMZ

- To assess the preliminary anti-tumor activity of BBI608 when administered in combination with TMZ
- To determine the pharmacodynamics (i.e., identify biomarkers) of BBI608 administered in combination with TMZ

Phase II:

To assess the disease control rate (DCR), median progression free survival (PFS), objective response rate (ORR), and overall survival (OS) of BBI608 administered in combination with TMZ in patients with recurrent or progressed GBM

3. ENDPOINTS AND COVARIATES: DEFINITIONS AND CONVENTIONS

3.1. Primary Endpoints

3.1.1. Phase Ib

Dose Limiting Toxicities (DLTs): For definition of DLT, see section 4.5 of Protocol [1].

3.1.2. Phase II

Progression free survival (PFS) at 6 months of BBI608 administered in combination with TMZ: is defined as the proportion of patients who have survived without objective disease progression per RANO criteria for at least 6 months after enrollment.

3.2. Secondary Endpoints

3.2.1. Phase Ib

- PK parameters of BBI608 administered in combination with TMZ
- Objective tumor response, as assessed using the Response Assessment in Neuro-Oncology (RANO) (4)
- Pharmacodynamic parameters (or biomarkers in archival tumor tissues), if identified appropriately, of BBI608 administered in combination with TMZ

3.2.2. Phase II

- Disease control rate (DCR), objective response rate (ORR), progression free survival (PFS), and overall survival (OS) of BBI608 administered in combination with TMZ (see 10.1 for Response Criteria and PFS/OS definitions).

3.3. Safety Endpoints

3.3.1. Adverse Events and Laboratory Abnormalities in Phase 1b and Phase 2

- Adverse Events (AEs) as characterized by type, frequency, severity (as graded by National Cancer Institute Common Terminology Criteria for Adverse Events [NCI

CTCAE] version 4.0), seriousness, and relationship to study therapy

- Other safety endpoints include physical examination, electrocardiogram (ECG) and vital sign data

3.4. Covariates

Demographic and baseline disease characteristics may be considered as covariates in population PK, PK/PD (biomarker) and anti-tumor efficacy exploratory analyses.

4. HYPOTHESES AND DECISION RULES

4.1. Statistical Hypotheses

There is no hypothesis testing in this study.

4.2. Statistical decision rules

4.2.1. Phase Ib

4.2.1.1. Dose escalation and de-escalation

Dosing of BBI608 in each arm of this trial will be initiated at 480 mg twice daily; this dose is the monotherapy RP2D for BBI608 and is also the RP2D of BBI608 in combination with weekly paclitaxel or capecitabine. The BBI608 dose can be modified according to the following schedule:

Dosing Level	Description
Initial Dose	480 mg twice daily (960 mg total daily)
Modification Level –1	240 mg twice daily (480 mg total daily)
Modification Level—2	80 mg twice daily (160 mg total daily)
Modification Level—3	80 mg once daily (80 mg total daily)

The dose of TMZ can be escalated from 150 mg/m² daily to 200 mg/m² daily as per standard TMZ dosing guidelines for patients who complete at least one cycle at 150 mg/m².

Number of Subjects with DLT at a Given Dose Level for a Given Study Arm	Dose De-escalation Decision Rule
≤ 1 out of 6	This dose level will be considered RP2D for the combination regimen (BBI608+TMZ)
≥ 2 out of 6	Initial dose level will be reduced to a dose chosen by the Investigator and BBI medical monitor. Six (6) additional subjects will be entered at this lower dose level and evaluated for DLT over the first 28 days of combination therapy.

